4.1 Compliance

Compliance will be quantified by (i) counts and proportion of participants who ate 75% or more of study foods. The data will be reported by treatment group and overall.

4.2 Secondary Endpoints

We will examine the effect of the low sodium diet on the following additional outcomes, testing the null hypothesis that there is no difference in the following outcomes between the low sodium diet and usual sodium diet intervention. We will examine the distribution of all variables. We will use linear regression for normally distributed outcomes and logistic regression for binary outcomes with and without adjustment for baseline. Continuous variables with non-normal residuals will be log-transformed with effects reported as a % change. If residuals are still not normally distributed even after log transformation we will apply non-parametric approaches.

- A. Seated diastolic blood pressure (average of two measurements days 12 and 14)
 - Continuous variable, normal distribution; as a sensitivity we will also examine last diastolic blood pressure measurement alone
- B. Standing blood pressure
 - Continuous variable, normal distribution

- C. Orthostatic hypotension
 - Binary variable, binomial distribution
- D. Timed Up and Go Test
 - Continuous variable, normal distribution
- E. Urinary sodium concentration, potassium concentration, sodium/creatinine ratio, potassium/creatinine ratio, and sodium/potassium ratio
 - These may require log-transformation; anticipate continuous variables, normal distribution
- F. Orthostatic symptoms
 - Binary variables (severe vs not), binomial distribution
- G. Side effects (5-point Likert scale)
 - Depending on the distribution of responses, side effect data will be analyzed as a continuous variable or dichotomized (none or any symptoms)

5 Missing data

We will employ a number of recommended strategies to prevent missing data:

- A simplified data collection schedule that minimizes participant burden;
- Intention-to-treat analysis that includes following participants according to the data collection schedule regardless of compliance with the study intervention;
- Frequent engagement with the participants through visit reminder calls or notes;
- A 24-hour phone number that participants can contact for questions and support;
- Contiguous windows of time during which specific follow-up visits are allowed;
- Monetary incentives to encourage enrollment and continued participation;
- Rigorous training of clinic staff emphasizing the importance of
 - Positive and warm interpersonal relationships between the participants and study staff
 - Study commitment during the consent process to ensure that potential participants understand the importance of completing the study
 - Addressing participant concerns to minimize dissatisfaction
 - Collecting data even if a participant discontinues the study treatment
 - Reasons for any drop-outs will be documented.

We will perform the following sensitivity analyses using established methods for addressing missingness in clinical trials: multiple imputations, best and worst-case scenarios, and use of the drop out event as a study end-point.³ We will compare the results from these approaches with primary analysis results to assess the primary result's robustness to the effects of missing data. Further, we will compare the baseline characteristics of complete cases and participants with missing measures between the two assignments.

6 Safety outcomes

We will compare self-reported symptoms that are thought to potentially arise from the diets. The symptoms will be summarized by the counts and proportions of participants in each group and overall. The treatment groups will be compared with respect to safety outcomes by using a chi-square test (Fisher exact test when there are cell counts less than 5).

7 References

3. Shih W. Problems in dealing with missing data and informative censoring in clinical trials. *Curr Control Trials Cardiovasc Med*. 2002;3(1):4.

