## SYNOPSIS

Elevated blood pressure (BP) affects virtually all adults over the age of 65 years in the United States and is a risk factor for both cardiovascular events and falls, which are common causes of long-term disability and premature death. Many older adults have limited mobility and experience food insecurity, relying on others for food preparation. Further, meals prepared for older adults are often high in sodium to overcome age-related declines in taste. Because of this, the Centers for Disease Control declared reduced-sodium meal plans in congregate living facilities a priority to combat the hypertension epidemic among older adults. However, many dietitians and health practitioners worry that low sodium in older adults could result in orthostatic hypotension (OH), causing impairments in physical function and consequently falls. Beyond BP there is evidence that sodium intake directly influences balance, seated-to-standing transitions, and gait speed. However, to date there are no clinical trials of the effects of sodium reduction on physical function.

We intend to perform an individual level randomized clinical trial at a community-based, congregate senior living facility that compares a reduced sodium meal plan (<0.9 mg per kcal of energy intake) to their typical meal plan (~2 mg per kcal of energy intake). This proposal has the following aims: (1) to determine the short-term effects of sodium reduction on BP regulation and OH, a hypothesized mechanism by which sodium intake might affect physical function; (2) to determine the short-term effects of a reduced sodium diet on physical function; and (3) to establish the premise for a longer-term trial by examining diet compliance, tolerability, and palatability. Ultimately, our two-tailed hypothesis ensures a high impact result long-term, since no effect on physical function would reinforce the safety of sodium reduction for cardiovascular disease prevention, while a positive relationship would reinforce a cautious approach to sodium reduction in this population. Beyond our scientific aims, our proposal will result in the development of a reduced sodium meal plan, using the leading food industry design platform, which can be readily implemented in a standardized fashion at long-term, senior care facilities throughout the country.

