## Objectives

*Specify the primary and secondary objectives.*

Virtually all older adults have hypertension, a known contributor to both cardiovascular disease and falls. The Centers of Disease Control has advocated for low sodium, senior meal plans as a strategy to lower BP.(1) However, the long-term effects of low sodium intake on physical function are largely unknown in older adults. Our pilot proposal for a randomized feeding study of a low sodium meal plan in a community-based, congregate senior living facility, will not only establish the premise for a definitive long-term trial on sodium reduction and physical function in older adults, but further contribute to a translatable, standardized menu that can be implemented *en masse* at senior living facilities throughout the U.S. Our long-term goal is to discover dietary interventions that enhance physical function as adults age. The objective of this proposed pilot study is to determine the feasibility of an individual-level, randomized feeding study that examines the impact of sodium reduction on BP regulation among semi-independent, older adults. Our central hypothesis is that sodium reduction will reduce seated BP without causing OH. Improved BP regulation will enhance circulatory function, efficiency of dynamic transitions from seated to standing positions, and ultimately a lower risk of falls.

**Primary Aim 1:** To determine the effects of a low sodium (<0.9 mg per kcal of energy intake), 2-week meal plan compared with a usual meal plan (average sodium ~2 mg per kcal of energy intake) on seated BP among independently living older adults.

**Hypothesis Aim 1:** *Compared with the usual meal plan, a reduced sodium meal plan will lower seated BP in older adults after 2 weeks.*

**Feasibility Aim 1:** To evaluate the recruitment experience, meal cost, meal delivery logistics, and compliance with and tolerability of the meal plan (urine sodium and palatability questionnaires).

**Feasibility Aim 2:** To determine effect size (variance) of secondary outcomes: standing BP, OH (standing minus seated BP), orthostatic symptoms, and a timed up and go test (TUG).

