### 1.2 Secondary Objectives

**Feasibility Aim 1:** To evaluate the recruitment experience, meal cost, meal delivery logistics, and compliance with and tolerability of the meal plan (urine sodium and palatability questionnaires).

**Feasibility Aim 2:** To determine effect size (variance) of secondary outcomes: standing BP, orthostatic hypotension (OH, standing minus seated BP), orthostatic symptoms, and a timed up and go test (TUG).

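### The aim asks for the effect and variance of the standing-minus-seated BP difference, but both analysis sections treat OH only as yes/no, so no planned analysis supplies them

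*SAP*

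**What the plan says.** - **The aim.** Feasibility Aim 2 (protocol Synopsis, Objectives; repeated in 1.2) is to determine "effect size (variance) of secondary outcomes: standing BP, OH (standing minus seated BP), orthostatic symptoms" and the timed up and go test. OH is therefore introduced as a difference between two pressures, which is a continuous quantity.
- **The use.** SAP 1.2 asks for effects and variances of the secondary outcomes. SAP 3.2 says they will feed the power calculations of later proposals and names OH in particular.
- **The analysis.** SAP 4.2 and protocol 9.5 both list OH as "Binary variable, binomial distribution". Orthostatic symptoms are "Binary variables (severe vs not), binomial distribution". The SAP's model rule is "We will use linear regression for normally distributed outcomes and logistic regression for binary outcomes with and without adjustment for baseline".
- **What stays continuous.** Standing blood pressure is listed in SAP 4.2 as "Continuous variable, normal distribution". Seated systolic pressure (primary) and seated diastolic pressure (secondary) are also analysed as continuous.
- **What is not stated.** Neither document gives the cut-point that turns the difference into yes/no OH, defines severe symptoms, or names the response scale for orthostatic symptoms. Neither plans a model for the difference.
- **Schedule.** The table in protocol 6.1 places the OH assessment at screening and at Visit 6. The Visit 6 list in 6.2.4 omits it.

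**The concern.** A logistic regression of yes/no OH yields an odds ratio and two proportions. It does not yield a mean postural change, a between-arm difference in mm Hg, or an SD, and these are what the aim asks for and what a later trial would need if it used the difference as its endpoint.

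The yes/no version is also the less precise one, and the sample is small. With about 40 people, OH cases may be few enough that an arm has none, and an ordinary logistic model then has no finite treatment estimate.

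OH is not incidental to this trial. The protocol's Objectives section states: "Our central hypothesis is that sodium reduction will reduce seated BP without causing OH".

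**Working it through.** **Inputs from the documents.** SAP 3.2: difference 9.53 mm Hg, SD 10.46, type 1 error 0.05, power 80%, 20 per arm, 45 recruited for 10% attrition. Neither document gives a sample size, power, prevalence or significance level for OH.

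**Inputs assumed.** OH prevalence from 5% to 50%; a normally distributed standing-minus-seated difference; two-sided 0.05.

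**1. The plan's own sample size.** By the normal approximation, n per arm = 2 × [10.46 × (1.960 + 0.842) / 9.53]² = 18.9, so 19. With the t distribution, power is 78.0% at 19 and 80.2% at 20, which gives the stated 20. Attrition: 40 / 0.9 = 44.4, so 45. The figures reproduce, and 20 per arm is used below.

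**2. Can the SD of the difference be recovered from the planned models?** Var(standing − seated) = Var(standing) + Var(seated) − 2 Cov(standing, seated). The planned models supply the two variances but not the covariance. Subtracting one treatment effect from the other could give a point estimate, but without the covariance it has no standard error.

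**3. Information kept by a yes/no cut.** For prevalence p, the efficiency relative to the continuous outcome is φ(z_p)² / [p(1 − p)]. At p = 0.10: 0.1755² / 0.09 = 0.342.

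| Assumed prevalence | Kept | Lost | 40 people act like |
|---|---|---|---|
| 50% | 64% | 36% | 25.5 |
| 30% | 58% | 42% | 23.0 |
| 25% | 54% | 46% | 21.5 |
| 20% | 49% | 51% | 19.6 |
| 10% | 34% | 66% | 13.7 |
| 5% | 22% | 78% | 9.0 |

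The loss reaches one half at a prevalence of about 21%.

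**4. Power for one illustrative shift.** Suppose OH goes from 10% to 30%. On the underlying normal scale, d = −0.524 − (−1.282) = 0.757. With 20 per arm the noncentrality is 0.757 × √(20/2) = 2.39.

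| Analysis | Power |
|---|---|
| Continuous difference, t test | 65% |
| Yes/no, logistic Wald (zero cells counted as non-significant) | 19% |
| Yes/no, Fisher exact | 24% |
| Yes/no, score test | 36% |

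The yes/no figures come from summing over all outcomes of two binomials with n = 20. The tests are unadjusted. The Wald figure is closest to the planned model.

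**5. Empty arms.** If diet has no effect, P(no case in at least one arm of 20) = 1 − [1 − (1 − p)²⁰]².

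| Prevalence in both arms | Expected cases in 40 | P(an arm with none) |
|---|---|---|
| 20% | 8 | 2% |
| 10% | 4 | 23% |
| 5% | 2 | 59% |

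An empty arm makes the logistic treatment estimate infinite. SAP 4.2 names no fallback for this.

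**6. Symptoms.** The scale is not stated, so this is illustration only. On a five-category scale with proportions q, under proportional odds, a cut with share s at or above it keeps 3s(1 − s) / (1 − Σq³).

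- Even spread, 40% severe or worse: 0.72 / 0.96 = 0.75, a 25% loss.
- Proportions 50, 25, 15, 7 and 3%, so 10% severe or worse: 0.27 / 0.856 = 0.316, a 68% loss. Any versus none keeps 0.75 / 0.856 = 0.877.

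Any versus none is the better cut when severe symptoms are rare. In the even-spread case it keeps only 0.50, so the recorded scale is the safer choice.

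**The case against.** **Most of the postural data are kept.** Standing, seated systolic and seated diastolic pressure are all continuous outcomes. Symptoms are also covered elsewhere: lightheadedness on standing is a solicited event (protocol 7.3), SAP 4.2 item G allows a continuous or none/any analysis of side effects, and SAP 6 uses Fisher's test for small cells. This stands. It limits the point to the within-person difference, but that is the quantity named in the aim.

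**This is a secondary outcome in a pilot.** Low power is expected there. That is fair, and low power alone would not be a finding. The mismatch between aim and analysis does not depend on power.

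**A reader might infer that half or more of the information is certainly lost.** The documents do not support that. Protocol 2.2 calls OH highly prevalent among older adults, which points to the smaller losses; the exclusion of low standing systolic pressure in 4.2 points the other way. Only a range can be given.

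**A reader might infer that an arm with no severe symptoms is likely.** That needs a severe-symptom rate near 5% or lower in each arm, and neither document gives one. At 10% the chance is 23%, and at 20% it is 2%.

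**A reader might infer that a non-significant OH result is going to be presented as proof of safety.** Neither document says so. The Synopsis sentence that comes closest, "no effect on physical function would reinforce the safety of sodium reduction", is about physical function, so it cannot carry a point about OH.

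**Conclusion.** The point holds as a mismatch between aim and analysis. The protocol asks for the effect and variance of a continuous difference, the SAP relies on that variance for planning, and no planned analysis produces it. This part needs no assumption from outside the documents.

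The cost in precision does depend on assumptions. For a normally distributed difference, the yes/no analysis loses about a third of the information at best, and half or more if prevalence is about 21% or lower. The contrast of 65% with 19% or 24% power applies to one assumed rise, from 10% to 30%, at two-sided 0.05; other shifts give other figures. Failure of the logistic model through an empty arm is a real possibility at 5–10% prevalence and a remote one at 20%.

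The missing OH cut-point and the missing definition of severe are gaps in their own right, because the binary variables cannot be reproduced without them. The change should be made before analysis, but it does not touch the primary result.

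**What to change.** 1. In SAP 4.2 and protocol 9.5, add the Visit 6 standing-minus-seated SBP and DBP differences as continuous outcomes. Analyse each by linear regression adjusted for the screening difference, and report the effect, its 95% CI and the SD.
2. Keep binary OH as a supporting result. State its cut-point, and report counts by arm with an exact CI.
3. State the response scale for orthostatic symptoms. Analyse them on that scale, or as any versus none, instead of only severe versus not; if the severe category is kept, define it.
4. Reconcile the Visit 6 list in protocol 6.2.4 with the table in 6.1, which schedules the OH assessment at that visit.

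The cost is wording in the two documents. The OH assessment is already scheduled at screening and Visit 6, so no visit or measurement is added.
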